#### 1- Introduction/Background/Purpose:

In the United States, preterm premature rupture of membranes (PPROM) complicates 4% of pregnancies annually. This pregnancy complication is a major contributor to preterm births and results in neonatal morbidity and mortality. Without treatment, 70-80% of women deliver within the 1st week following membrane rupture. Multiple trials have proven that antibiotics given to this population prolong the latency from time of PPROM to delivery, hence reducing maternal and neonatal morbidities.

According to the American College of Obstetrics and Gynecology, the current standard of care for PPROM subjects between the gestational age of 24 weeks and 0 days and 33 weeks and 6 days, is to administer ampicillin 2 gm IV every 6 hours for 48 hours followed by amoxicillin 250 mg orally every 8 hours for 5 days, with erythromycin 250 mg IV every 6 hours for 48 hours followed by 500 mg orally every 8 hours for 5 days. In this regimen, multiple doses of intravenous (IV) and oral (PO) doses of erythromycin are needed to achieve the desired outcome. Erythromycin can cause GI upset and some subjects do not tolerate this regimen over the course of 7 days. In addition, there is a national shortage of erythromycin, and published expert opinion proposed to use a second-generation macrolide (azithromycin) instead of erythromycin. This strategy was adopted nationwide including our maternal center at UTMB since 2014. Compared to erythromycin, advantages of azithromycin include:

- It is taken once orally (due to its long intracellular half-life).
- The entire regimen is much cheaper than the multiple does of erythromycin (23 doses).
- It has less gastrointestinal adverse effects.

As a result, azithromycin is now commonly being used as a substitute for erythromycin on many labor and delivery units around the country.

Despite its common use, there exists no level 1 evidence that azithromycin is equivalent to erythromycin. Haas and colleagues published a retrospective comparison of the two regimens in 2014 and concluded that the substitution of azithromycin for erythromycin in the recommended antibiotic regimen did not impact latency or any other measured maternal or fetal outcomes. This study, however, was limited by its non-randomized retrospective nature. Our objective is to compare the effectiveness of the 2 regimens in prolonging pregnancy after PPROM.

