#### 3.3. Antibiotics Disposal and Administration

Once a subject is consented and randomized, the appropriate antibiotics according to group assignment will be dispensed by the regular hospital pharmacists after order is placed in EPIC (as part of standard procedure at UTMB). Both drugs are standard of care at UTMB. This is a pragmatic/comparative effectiveness of two standard of care therapies. Regular hospital pharmacy currently stores and disposes the drugs and subject's insurance will be responsible for paying for either antibiotic, as any other subject not in the study. Floor nurses will be administering antibiotics. Research staff will be checking medication administration record (MAR) in EPiC for compliance to the research protocol; if an antibiotic is withheld for any reason the staff will inform the PI and report it as a protocol deviation which may potentially affect the integrity of the data for that subject.

The subject will be included in the analysis by intent-to-treat once the assigned antibiotics are dispensed from inpatient pharmacy and sequential number posted on the subject specific randomization form.

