#### 3.6. Withdrawals

Subjects who withdraw from the study after randomization will be excluded from further follow-up. Outcomes ascertained up until the time of withdrawal will be reported in an intent to treat fashion. Those who withdraw prior to determining the primary outcome will be accounted for by randomizing an equal number of additional subjects.

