# 12-Potential benefits:

In the background of erythromycin nationwide shortage, this will be the first level 1 trial to show that azithromycin may be equivalent to erythromycin in delaying delivery in patients with PPROM. This study may show for the first time that current alternative practice with azithromycin is as effective as erythromycin but with less adverse effects, less costly and easy administration.

13-**Statistical approach:** Analysis will be performed by intent to treat. Univariable analysis (such as t-test, Mann-Whitney or Chi-square) will be used for descriptive statistics such as patient demographics and assessment of primary outcome. Multivariable logistic analysis will be used to account for potential confounding variables. Sample size was calculated using a noninferiority trial design. Azithromycin will be tested against erythromycin for PPROM. The primary outcome will be the proportion of subjects undelivered

by day 7. For the sample size calculation, it is assumed the proportion undelivered in the erythromycin group would be 70% (pi = 0.7) based on Haas et al study. We considered that a difference in undelivered rate as large as 15% in favor of erythromycin would allow azithromycin to be non-inferior (delta = 0.15). This study will use 80% power to confirm non-inferiority and a one-sided confidence level of 97.5%.

Estimated sample size for two-sample comparison of proportions (non-inferiority)

Null hypothesis: p2 - p1 � delta (inferior), where:

pi (entered in command) is the overall proportion of participants expected to experience the outcome if the treatments are non-inferior, and delta is the smallest change in proportions between groups (p2 - p1) which would still be clinically important.

Alternative hypothesis: p2 - p1 < delta (non-inferior)

Note: a non-inferiority analysis is one-sided.

```
Assumptions:

power = 0.8000

alpha = 0.0250 (one-sided)

pi = 0.7000

delta = 0.1500

estimated required sample size (per group) = 147
```

The total estimated sample size is 294. Assuming 10% loss to follow, this study proposes a total of 324 subjects will be needed to complete the study. The STAT 14 (Dallas, Tx) will be used for statistical computations. This trial will be registered with Clinical Trials Register (Clinicaltrials.gov), before recruitment is initiated and after IRB approval."

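### Intent-to-treat is the only analysis planned for a non-inferiority claim, with 1 versus 23 macrolide doses; a supportive adherence analysis should be pre-specified

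*Combined protocol and SAP*

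**What the plan says.** Section 13 (Statistical approach) sets the design: "Sample size was calculated using a noninferiority trial design", with a 15-point margin, 80% power and one-sided alpha of 0.025. The analysis population is given in one sentence: "Analysis will be performed by intent to treat". No per-protocol, as-treated or adherence-adjusted analysis appears anywhere in the document.

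The intent-to-treat set is not all randomised women. Section 3.3 says: "The subject will be included in the analysis by intent-to-treat once the assigned antibiotics are dispensed from inpatient pharmacy". Section 3.6 adds: "Those who withdraw prior to determining the primary outcome will be accounted for by randomizing an equal number of additional subjects".

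On adherence, section 1 says of erythromycin that "some subjects do not tolerate this regimen over the course of 7 days" and that "there is a national shortage of erythromycin". Section 7.3 lists nausea and vomiting at 25% with erythromycin and 3% with azithromycin. Section 3.3 provides for monitoring: "Research staff will be checking medication administration record (MAR) in EPiC for compliance to the research protocol". A withheld antibiotic is reported as a protocol deviation that may affect the integrity of that woman's data. No analysis uses this information.

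**The concern.** In a superiority trial, non-adherence usually dilutes the effect and works against the claim. In a non-inferiority trial, dilution makes the arms look alike and works for it. Here the room for departure is mostly on one side: azithromycin is one dose at randomisation, while erythromycin runs over seven days. If azithromycin were truly worse when both drugs are taken as assigned, women in the erythromycin arm who stop or switch, and lose benefit by doing so, would lower the comparator's rate and shrink the observed deficit.

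Section 12 looks forward to showing that azithromycin is as effective as erythromycin. With intent-to-treat alone, a reader of a positive result could not tell whether it reflects the drug or an incompletely delivered comparator.

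**Working it through.** **Inputs from the documents.** Erythromycin rate undelivered at day 7: 0.70. Margin: 0.15. One-sided alpha: 0.025. Power: 0.80. Allocation: 1:1 (sections 4 and 13).

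**Dose counts.** Erythromycin every 6 hours for 2 days is 8 doses, and every 8 hours for 5 days is 15, so 8 + 15 = 23, as section 1 states. Azithromycin is 1.

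**The plan's sample size.** n per arm = 2 × 0.7 × 0.3 × (1.960 + 0.842)² / 0.15² = 146.5, rounded up to 147. This reproduces the stated figure. The total is 294, and 294 × 1.1 = 323.4, which gives the stated 324.

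**Inputs assumed.** The documents give neither of these:
- f, the share of the erythromycin arm that departs from the assigned macrolide;
- q, the proportion of those women still undelivered at day 7.

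**Model.** Put the drugs as taken exactly at the margin: erythromycin 0.70, azithromycin 0.55. Under intent-to-treat the erythromycin arm then has rate pE = 0.70(1 − f) + q·f, against pA = 0.55. Non-inferiority is claimed when the lower limit of the two-sided 95% CI for azithromycin minus erythromycin exceeds −0.15. With SE = √[pE(1 − pE)/147 + pA(1 − pA)/147],

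P(claim) = Φ{[0.15 − (pE − pA)]/SE − 1.96}.

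**Example, f = 0.20 and q = 0.55.** pE = 0.67 and the difference is 0.12. SE = √[(0.2211 + 0.2475)/147] = 0.0565. Then 0.03/0.0565 − 1.96 = −1.43, and Φ = 7.7%.

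| f | q = 0.70 | q = 0.55 | q = 0.40 |
|---|---|---|---|
| 0 | 2.5% | 2.5% | 2.5% |
| 5% | 2.5% | 3.4% | 4.5% |
| 10% | 2.5% | 4.5% | 7.7% |
| 20% | 2.5% | 7.7% | 18.2% |

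The q = 0.70 column is constant because pE stays at 0.70. Exact binomial enumeration gives nearly the same values: 4.3% for 4.5%, 7.4% for 7.7%, and 17.9% for 18.2%.

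**A simple per-protocol set has its own bias.** Women who deliver early have less time to stop. Suppose, for illustration, that 20% of undelivered and 10% of early-delivering erythromycin women stop, with no effect on outcome. The retained erythromycin rate is (0.70 × 0.80)/(0.70 × 0.80 + 0.30 × 0.90) = 0.56/0.83 = 67.5%, a fall from 70% by selection alone. With 0.83 × 147 = 122 women against 147 at 55%, the same formula gives about 6.3%. This bias runs in the same direction as the one the analysis is meant to detect.

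**Power of the supportive analysis.** With both true rates at 0.70, dropping 10% of the erythromycin arm leaves 132.3 women: Φ{0.15/√[0.21/132.3 + 0.21/147] − 1.96} = 78%. Dropping 20% leaves 117.6 and gives 75%.

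**The case against.** The strongest reply is that the trial calls itself pragmatic (sections 2 and 3.3). Better tolerability and simpler dosing are among the stated advantages of azithromycin, so they belong to the comparison. In the example above, the difference as assigned is 67% versus 55%, or 12 points, which is inside the margin. For that question non-inferiority is true, and intent-to-treat still holds 2.5% at its own boundary. This stands. A reader might infer that intent-to-treat is the wrong primary analysis, or that the stated one-sided 2.5% is already breached; the documents support neither.

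A reader might also infer that crossover from erythromycin to azithromycin is documented. It is not. Section 1 describes substitution as a practice adopted by institutions during the shortage, and section 3.3 speaks of withheld antibiotics, not swapped ones. The shortage is also a weak source of dilution in the analysed set as defined, since a woman whose erythromycin was never dispensed would not enter it.

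Finally, nurses give the drugs and staff check the records, so non-adherence may be modest. About 30% of women are assumed delivered by day 7, and many of them would never be due all 23 doses. What remains is mid-course intolerance, which the protocol itself expects, and an adherence record that no analysis uses. If non-adherence proves small, the supportive analysis will probably agree and strengthen the claim.

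**Conclusion.** The gap is a missing supportive analysis, not a demonstrated inflation of error. Intent-to-treat alone could overstate non-inferiority for the drugs as taken. Across the assumed range of 10% to 20% non-adherence, the chance of the claim at a true 15-point deficit runs from 2.5% (non-adherers still at 70%) to 18.2% (20% non-adherent, at 40%). The documents fix neither the rate nor the outcome, so no single figure can be put on the effect. The direction holds only if departures occur mainly in the erythromycin arm, or about equally in both, and cost benefit. Departures in the azithromycin arm alone would work the other way, though a single dose at randomisation leaves little room for them. This is a cheap improvement to the plan.

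**What to change.** 1. Define the primary intent-to-treat set as all randomised women, not from dispensing. Do not substitute replacements for withdrawn women; keep the withdrawn women in the set.
2. Pre-specify a supportive adherence analysis from the medication administration record. Before the data are seen, define adherence as receipt of the assigned macrolide doses due while still undelivered, up to day 7. Stopping and switching then both count as departures, and early delivery does not.
3. Allow for the shorter time that early-delivering women have to depart, for example by censoring at departure with inverse-probability weighting on collected covariates such as gestational age at rupture, tocolytics and antenatal steroids. Otherwise, report the simple per-protocol result with this selection bias stated.
4. Compare the two-sided 95% CI with the same −15 point margin. If intent-to-treat meets the margin and the adherence analysis does not, report non-inferiority as not robust.
5. Report adherence by arm.

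The cost is SAP wording and additional analysis of records that staff already check. The supportive analysis is less precise (about 78% or 75% power if 10% or 20% of the erythromycin arm is dropped at 147 per arm), rests on assumptions that randomisation does not protect, and does not replace intent-to-treat.

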#### 2- Concise summary of project:

This trial will be a comparative effectiveness pragmatic multi-site randomized trial performed in singleton pregnancies with the diagnosis of PPROM between 24 weeks and 0 days - 32 weeks and 6 days. It will be comparing two well-accepted standardized treatments of care in this subject population: Erythromycin (FDA Category B) versus Azithromycin (FDA Category B). Our primary outcome will be the proportion of women still pregnant by day 7 after the diagnosis of PPROM is made. Our working hypothesis is that there is no measurable difference in the primary outcome between the group randomized to the azithromycin regimen versus the group randomized to the erythromycin regimen. Our secondary outcome will be latency defined as interval from PPROM to delivery. We propose a total of 324 subjects will be needed to complete the study.

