# 3.7 Outcomes

# Primary outcome:

• Proportion of undelivered subjects at day 7 from the diagnosis of PPROM

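### The trial is sized for non-inferiority with a 15-point margin, but the tests named for the primary outcome test zero difference and no rule compares a confidence limit with the margin

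*Combined protocol and SAP*

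**What the plan says.** The primary outcome in section 3.7 is binary: "Proportion of undelivered subjects at day 7 from the diagnosis of PPROM".

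Section 13 (Statistical approach) begins with the analysis. After committing to intent to treat it says: "Univariable analysis (such as t-test, Mann-Whitney or Chi-square) will be used for descriptive statistics such as patient demographics and assessment of primary outcome". It then adds: "Multivariable logistic analysis will be used to account for potential confounding variables".

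The same section then turns to sample size: "Sample size was calculated using a noninferiority trial design". The margin is put in words, namely that "a difference in undelivered rate as large as 15% in favor of erythromycin would allow azithromycin to be non-inferior", and the level follows: "This study will use 80% power to confirm non-inferiority and a one-sided confidence level of 97.5" per cent. Hypotheses involving delta are printed with the software output ("Alternative hypothesis: p2 - p1 < delta (non-inferior"), where p1 and p2 are not assigned to arms.

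Section 2 gives the hypothesis without a margin: "Our working hypothesis is that there is no measurable difference in the primary outcome".

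**The concern.** The design asks whether a loss of 15 points or more can be ruled out. The tests listed for the primary outcome ask whether the difference is zero. A non-significant result on the second question does not answer the first, because it can arise when the data are compatible with a loss well beyond 15 points. The logistic model does not close the gap. It has no margin on its odds-ratio scale, and its standing relative to the univariable test is not given.

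An analyst who follows the analysis sentence, read with section 2, could report a non-significant chi-square or odds ratio as the main finding. One who follows the sample-size paragraph would compare a confidence limit with the margin. The trial's headline conclusion depends on which is done, and the plan leaves that choice open until the data are in.

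**Working it through.** **Inputs.** All are from section 13 unless noted: erythromycin rate 0.70; margin 0.15 on the risk-difference scale; one-sided alpha 0.025; power 0.80; 147 per group; 324 in total after a 10% allowance, so 162 per arm at 1:1 allocation (section 4).

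**Step 1: reproduce the plan's figure.** n = 2 × 0.7 × 0.3 × (1.960 + 0.8416)² / 0.15² = 146.5, rounded up to 147 per group. The total is 294, and 294 × 1.10 = 323.4, giving 324. The trial is therefore sized for a comparison with the 15-point margin. A two-sided test of 70% against 55% would have given 163 per group.

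**Step 2: one data set, two analyses.** Take 103/147 (70.1%) undelivered on erythromycin and 90/147 (61.2%) on azithromycin.
- Difference: -0.0884.
- Chi-square: pooled rate 193/294 = 0.6565; standard error √(2 × 0.6565 × 0.3435 / 147) = 0.0554; z = 1.60; p = 0.11.
- Odds ratio: (90/57)/(103/44) = 0.67, 95% CI 0.42 to 1.10.
- Wald interval: standard error √[(0.7007 × 0.2993 + 0.6122 × 0.3878)/147] = 0.0552; lower limit -0.0884 - 1.96 × 0.0552 = -0.197. The score and Newcombe limits are -0.195 and -0.194.

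The first two results read as no significant difference. The interval says non-inferiority is not shown.

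**Step 3: how wide the disagreement is.** No success rule is assumed here. Against 103/147:

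| Azithromycin undelivered | Difference (points) | Chi-square p | Wald lower limit (points) |
|---|---|---|---|
| 87 | -10.9 | 0.051 | -21.7 |
| 90 | -8.8 | 0.110 | -19.7 |
| 96 | -4.8 | 0.383 | -15.4 |
| 97 | -4.1 | 0.453 | -14.7 (passes) |

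Every count from 87 to 96 is non-significant but fails the margin, whether the interval is Wald, score or Newcombe. At 162 per arm against 113 on erythromycin, the Wald range is 97 to 105 (9.9 to 4.9 points worse).

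**Step 4: how often.** Exact binomial enumeration over all pairs of counts, erythromycin 0.70, uncorrected chi-square, Wald limit. Each cell gives 147 / 162 per arm.

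| True deficit | P(chi-square p ≥ 0.05) | P(lower limit > -0.15) | P(non-significant and margin not excluded) |
|---|---|---|---|
| 0 | 0.9499 / 0.9506 | 0.8024 / 0.8398 | 0.1726 / 0.1354 |
| 5 points | 0.8477 / 0.8391 | 0.4515 / 0.4863 | 0.3983 / 0.3546 |
| 10 points | 0.5621 / 0.5264 | 0.1440 / 0.1562 | 0.4182 / 0.3703 |
| 15 points | 0.2411 / 0.2025 | 0.0237 / 0.0254 | 0.2174 / 0.1772 |

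At a true 20-point deficit the first two probabilities are 0.0582 / 0.0416 and 0.0020 / 0.0019. At 147 per arm and a 15-point deficit, an erythromycin rate of 0.60 gives 0.2555 against 0.0257, and a rate of 0.80 gives 0.1739 against 0.0252.

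**Step 5: the odds-ratio scale.** A 15-point deficit is (0.45/0.55)/(0.60/0.40) = 0.55 at an erythromycin rate of 60%, (0.55/0.45)/(0.70/0.30) = 0.52 at 70%, and (0.65/0.35)/(0.80/0.20) = 0.46 at 80%. No single odds ratio stands for the margin.

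**Step 6: direction of the printed hypotheses.** Remaining undelivered is the favourable outcome. The printed alternative agrees with the margin described in words only if p1 is azithromycin and p2 is erythromycin.

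**The case against.** The strongest reply is that section 13 is a single section and already holds the margin, its scale and direction, the one-sided level and hypotheses written with delta. The intent to test non-inferiority is plain. The list of tests is open-ended, covers demographics as well, and includes methods that cannot be meant for a yes/no outcome, so it is weak evidence that chi-square is the confirmatory test. The logistic sentence names no outcome. The hypothesis in section 2 may only state the expected truth, which matches the equal 70% rates behind the sample size. No passage says that a non-significant test counts as success.

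Much of this is fair. The intent can be inferred, the unlabelled p1 and p2 are a minor matter because the prose fixes the direction, and the odds-ratio point matters only if the logistic model is used to decide the question. The second column of the Step 4 table becomes an error rate only under a reading the documents do not state.

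The core is untouched. An open list that omits the needed method does not specify it, and the sentence that does assign a method to the primary outcome points to a test without a margin. The one-sided confidence level stands beside the power figure and is not tied to an estimate or a decision. The ranges in Step 3 need no assumption about how success is judged.

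**Conclusion.** The concern holds: the plan is wrong as written on this point. The only listed test that suits the primary outcome does not address the question the trial was sized to answer, and no interval or decision rule for the margin is given. With erythromycin at 103/147, azithromycin results from 4.8 to 10.9 points worse would be non-significant yet fail non-inferiority.

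If non-significance were read as reassurance, a true 15-point deficit would be passed 24.1% of the time at 147 per arm (20.3% at 162), against 2.4% (2.5%) under a confidence-limit rule. Those rates rest on that reading, a 70% erythromycin rate, the uncorrected chi-square and a Wald limit. The sample size itself is not in question. Because the gap governs the trial's main conclusion, it should be closed before the analysis.

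**What to change.** In section 13:
- Label the hypotheses. With p the proportion undelivered at day 7, H0: p(azithromycin) - p(erythromycin) ≤ -0.15; H1: p(azithromycin) - p(erythromycin) > -0.15.
- Make the primary analysis the risk difference with its two-sided 95% (one-sided 97.5%) confidence interval by a named standard method. Conclude non-inferiority only if the lower limit is above -15 points.
- State that chi-square and the multivariable logistic model are supplementary, and that a non-significant p-value is not evidence of non-inferiority.

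In section 2, restate the working hypothesis as non-inferiority within the margin. The equivalence wording in section 12 could be aligned at the same time. Section 1 need not change.

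The cost is a few sentences, with no extra patients or data. If both true rates are 70%, the rule has 80.2% power at 147 per arm and 84.0% at 162. The team should know that if azithromycin is truly 5 points worse, which is inside the margin, non-inferiority would be missed 54.9% of the time at 147 per arm (51.4% at 162). That follows from the existing margin and sample size, not from the edit.

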# Secondary outcomes:

• Latency defined as time interval from PPROM to delivery

Data to be collected will consist of demographics, obstetrical history, relevant vital signs and laboratories. Examples of data to be collected but not limited to include: age, ethnicity/race, gravida, para, received tocolytics, received antenatal steroids, gestational age at rupture of membranes, reason for delivery, mode of delivery, gestational age at delivery, chorioamniotis, date & time of initiation of antibiotics, date & time of delivery, placental abruption, hospital length of stay, number of women undelivered at day 7 of admission, NICU admission, infant intubation days, neonatal NEC and neonatal sepsis.

In addition, drug adverse effects profiles between the two will be assessed in a post treatment patient survey. The latter will be assessing the severity and incidence of diarrhea and other symptoms such as nausea and vomiting and their severity.

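### Gestational age at rupture is collected but has no stated role in the primary estimate; naming it as the covariate in a standardised risk difference would gain precision at almost no cost

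*Combined protocol and SAP*

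**What the plan says.** Section 13 (Statistical approach) calls for an intention-to-treat analysis and places the primary outcome under unadjusted methods: "Univariable analysis (such as t-test, Mann-Whitney or Chi-square) will be used for descriptive statistics such as patient demographics and assessment of primary outcome". The next sentence adds "Multivariable logistic analysis will be used to account for potential confounding variables". No covariate, selection rule or effect scale is given for that model. The section does not say which of the two analyses is compared with the margin.

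The margin is a difference in proportions: "a difference in undelivered rate as large as 15% in favor of erythromycin would allow azithromycin to be non-inferior (delta = 0.15". The sample-size output is likewise for an unadjusted difference: "estimated required sample size (per group) = 147".

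The data list under Secondary outcomes in section 3.7 includes "gestational age at rupture of membranes". Section 5 admits women from 23 6/7 to 32 6/7 weeks; section 2 starts the window one day later. It is about nine weeks either way. Neither section 3.2 nor the paragraph on centralised randomisation after the list of sites mentions balancing the arms on gestational age.

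**The concern.** Gestational age at rupture is fixed before randomisation, and it is plausibly related to whether a woman is still pregnant a week later. If it is, an analysis that leaves it out gives a wider interval than the same data could support. That matters here because the trial is sized at 80% power, and the result turns on whether the lower confidence limit clears -15 points.

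The logistic model does not fill the gap as written, for two reasons.

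- **Scale.** It yields an odds ratio, while the margin is in percentage points.
- **Open covariates.** The data list in section 3.7 is given as examples only, and it mixes baseline items with later events such as reason for delivery and chorioamnionitis. Clinical chorioamnionitis at randomisation is an exclusion (section 6), so a recorded case would arise afterwards. Nothing in section 13 keeps such variables out of the model or fixes the choice before the data are seen.

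With two analyses and no stated precedence, a result near the margin could have two answers.

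**Working it through.** **Inputs from section 13:** 70% undelivered in both arms, margin 0.15, one-sided alpha 0.025, power 80%, 147 per group.

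**1. Reproduce the plan's figure.** n = 2 × 0.7 × 0.3 × (1.960 + 0.842)² / 0.15² = 146.5, rounded up to 147. This agrees with the plan.

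**2. Unadjusted precision at 147 per arm.** SE = √(0.42/147) = 0.0535, or 5.35 points. The 95% half-width is 1.96 × 5.35 = 10.5 points, so an observed azithromycin deficit above about 15 - 10.5 = 4.5 points fails. Power = Φ(0.15/0.05345 - 1.96) = 80.1%.

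**3. Adjusted precision.** Let R² be the share of outcome variance explained by gestational age. The documents do not give it, so a range is assumed. The SE becomes approximately 5.35 × √(1 - R²), and power is Φ(0.15/SE - 1.96). Two simulation runs at 147 per arm, using a logistic model averaged to a risk difference, check the formula. Run 1 used 3,000 trials per setting and assumed odds ratios per SD of gestational age of 1.5, 2.0 and 2.5 for the last three rows.

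| Assumed R² | Formula SE (points) | Formula power | Run 1, unadjusted to adjusted | Run 2, unadjusted to adjusted |
|---|---|---|---|---|
| 0 | 5.35 | 80.1% | not run | 80.0% to 79.7% |
| 0.03 | 5.26 | 81.3% | 79.3% to 80.6% | 79.8% to 81.1% |
| 0.09 | 5.10 | 83.7% | 80.4% to 83.7% | 79.3% to 82.5% |
| 0.14 | 4.96 | 85.7% | 81.3% to 86.1% | 80.2% to 85.0% |

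The simulation error of a power near 80% from 3,000 trials is √(0.8 × 0.2/3000), about 0.7 points, so differences of a point between columns mean little. The formula gives 84.1% at R² = 0.10 and 86.1% at 0.15. At R² = 0.10 the adjusted analysis would need 0.9 × 146.5 = 131.9, so 132 per arm, for the original 80% power. In a further simulation the adjusted analysis kept one-sided type I error at 2.2% to 2.8%.

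**4. Two analyses, one margin.** In run 1 the adjusted and unadjusted non-inferiority conclusions differed in 4.3%, 6.3% and 8.0% of trials at R² of 0.03, 0.09 and 0.14. At R² = 0.01 they differed in 2.0%.

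**5. Why an odds ratio does not fit the margin.** At 70% undelivered with erythromycin, a 15-point deficit is 55%, an odds ratio of (0.55/0.45)/(0.70/0.30) = 0.52. If the erythromycin rate were 80%, the same 15 points would be (0.65/0.35)/(0.80/0.20) = 0.46. At 60% it would be (0.45/0.55)/(0.60/0.40) = 0.55. No single odds ratio stands for 15 points, so the model result has to be averaged back to a risk difference.

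**The case against.** The strongest reply is that nothing is broken. The unadjusted comparison matches the sample-size calculation, and randomisation makes it valid. An adjusted model is already planned, and the text does not exclude gestational age from it. The gain may also be slight: at R² = 0.01, run 1 moved power only from 80.3% to 80.4%. If all 324 women contribute (162 per arm), unadjusted power is already 83.8%. All of this stands, and it limits the point to efficiency and pre-specification.

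Three stronger readings are tempting, and the documents do not support them.

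- A reader might infer that covariates will be picked from baseline significance tests, because demographics and the primary outcome share a sentence and the logistic model follows. Section 13 gives no selection rule and does not link the two. Dropping the baseline tests would change no primary result.
- A reader might infer that chance imbalance in gestational age could create or hide non-inferiority. An imbalance beyond 0.2 SD in either direction has probability 0.086 (SD of the imbalance = √(2/147) = 0.117). That variation is already in the unadjusted standard error, so type I error is not inflated.
- A reader might infer that cervical dilation could be added from data in hand. It appears only as an eligibility threshold in section 5. It is not among the listed data items, although that list is not exhaustive.

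**Conclusion.** The point holds as an inexpensive improvement, not as the correction of an error. The textual facts are clear: the primary comparison is unadjusted, the model's covariates are unnamed, its natural scale does not match the margin, and a recorded baseline variable has no stated role.

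The gain ranges from nothing to about 5 or 6 power points over R² from 0 to 0.15. Where the trial falls in that range depends on a prognostic strength that the documents do not supply. The figures also assume 147 analysed per arm and 70% undelivered in both. Because almost nothing is lost when gestational age is uninformative, the recommendation does not depend on knowing R². No change to the sample size follows.

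**What to change.** Before data lock, amend section 13 to state the following.

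1. The primary estimate is the difference (azithromycin minus erythromycin) in the proportion undelivered at day 7, standardised from a logistic model with arm and continuous gestational age at rupture.
2. Its two-sided 95% confidence interval, robust or by the delta method, is compared with -15 points. This analysis alone decides non-inferiority.
3. The unadjusted difference with its interval is reported as supportive.
4. Covariates are not chosen after seeing the data, and variables arising after randomisation are not used. Any further baseline covariate, such as site, is named at the same time.

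The cost is a few sentences and a few lines of code, with no new data, visits or participants. The one constraint is timing: the covariate has to be fixed before the data are seen.
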